2.0 Purpose

The statistical analysis plan (SAP) describes the statistical methods to be used during the reporting and analyses of data collected under Mirati Therapeutics, Inc. Protocol MRTX-500.

3.0 Scope

This plan is a living document that supplements the study protocol for statistical analysis-related aspects.

The SAP outlines the following:

- Study objectives and endpoints
- Study design
- Analysis populations
- Endpoint and variable definitions
- Data handling
- Data review
- Statistical methods

Deviations from the SAP will be described in the Clinical Study Report (CSR).

4.0 Introduction

This SAP describes the statistical methods to be used during the analysis and reporting of data collected under Mirati Therapeutics, Inc. Protocol MRTX-500.

This SAP should be read in conjunction with the study protocol and case report form (CRF). This version of the plan has been developed using the protocol v6.0 dated 11-Feb-2020 and CRF v4.0 dated 07-Jan-2020. Any further changes to the protocol or CRF may necessitate updates to the SAP.

The stable version of the SAP will be approved based on the current protocol and CRF, allowing programming to be initiated. A final version of the SAP will be issued for approval prior to database lock.

Each version of the SAP requires approval by the sponsor.

4.1 Changes from Protocol

4.1.1 Glesatinib

Enrollment into Glesatinib cohorts was discontinued in November 2017 as a result of Sponsor portfolio reprioritization. The analysis and reporting of this treatment arm is limited to the Lead-in phase only, and will be summarized for patient disposition, demographics, primary disease history, prior primary disease treatment, medical history, prior/concomitant medications and a single AE table only. Any other data will appear in listings only.

4.1.2 Mocetinostat

Enrollment into Mocetinostat cohorts was never initiated and therefore no analysis or reporting of this treatment arm is necessary. The reference to Mocetinostat will only remain in the SAP where text is copied verbatim from the protocol.

4.1.3 Analysis Populations

The modified Intent-to-Treat (mITT) population as defined in Section 9.3.1 of the protocol has been renamed as the Full Analysis Set (FAS).

Section 3.2 of the protocol described that for patients to be part of the Clinical Activity Evaluable (CAE) population they “...must have at least one on-study disease assessment or discontinue from treatment for progressive disease (PD) prior to this assessment.” This definition was modified by Mirati to be as described in Section 7.3 of this SAP, where it includes “patients with measurable disease (per RECIST 1.1) at baseline and have received at least one dose of both investigational study drug and Nivolumab, must have at least one on-study disease assessment or discontinue from treatment for PD.”

4.1.4 Clinical Benefit Rate (CBR)

Section 9.4.2 of the protocol states that “Clinical Benefit Rate (CBR) is defined as the percent of patients documented to have a confirmed Complete Response (CR), Partial Response (PR), or Stable Disease (SD) documented during at least 2 on-study assessments and including at least 14 weeks on study (e.g., allowance for 2-week window around Week 17 assessment).”

Amendments have been made to the later part of this definition to allow for at least one on-study assessment at least 42 days on study. This change is aligned with the definitions laid out in Section 8.2 in this SAP.

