9.4.2 Clinical Benefit Rate

Clinical Benefit Rate (CBR) is defined as the percent of patients documented to have a confirmed Complete Response (CR), Partial Response (PR), or Stable Disease (SD) documented during at least 2 on-study assessments and including at least 14 weeks on study (e.g., allowance for 2-week window around Week 17 assessment).

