**Confirmed Response Based on Subsequent Assessments*;**

First Time Point Response**	Second Time Point Response	Confirmed Response (Best Response)*
PD	No further evaluation	PD
NE	PD	PD
CR	PD	SD or PD (1)
PR	PD	SD or PD (1)
SD	PD	SD or PD (1)
CR	CR	CR
CR	NE **	SD or NE (2)
PR	CR	PR
PR	PR	PR
PR	SD (3)**	SD
PR	NE **	SD or NE (2)
SD	CR	SD
SD	PR	SD
SD	SD	SD
SD	NE	SD or NE (2)
NE	CR	SD
NE	PR	SD
NE	SD	SD
NE	NE	NE

* A Best Response of SD can only be made after the patient is on-study for a minimum of 42 days. If the patient is on-study less than 42 days, any tumor assessment indicating stable disease before this time period will have a Best Response of NE unless PD is identified.

** Subsequent documentation of CR may provide confirmation of a previously identified CR for patients where the second integrated response was NE. Subsequent documentation of PR may provide confirmation of a previously identified PR for patients where the second integrated response was NE or SD. If the third response confirms the CR (or PR) then the confirmed response will be CR (or PR).
For example: CR NE CR = CR; PR NE PR = PR.

Additionally, one SD is allowed between PRs (e.g., PR SD PR = PR).

- (1) Best response will be SD if the first response is after 42 days on-treatment. Otherwise, the best response will be PD.
- (2) Best response will be SD if the first response is after 42 days on-study. Otherwise, the best response will be NE.
- (3) Response is SD if the increase from the first to the second assessment does not qualify for PD.

For patients with unconfirmed CR/PR that can't be confirmed due to dropping off study, the best overall response will be SD.

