8.2.3 Clinical Benefit Rate (CBR)

CBR will be categorized in accordance with RECIST v1.1. CBR is defined as the proportion of patients documented to have a confirmed CR or PR, or SD.

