11.1.6.1 Primary Variable

Descriptive statistics for ORR and BOR (CR, PR, SD, PD and NE) based on the response assessments by the Investigator will be presented by treatment arm and strata. Exact 95% Clopper-Pearson CIs for ORR will also be presented.

An exact test for single proportion (one-sided $\alpha=0.025$) will be performed to test H_0 : ORR $\leq 5\%$ against H_1 : ORR $> 5\%$ for CIT-experienced and PD-L1 no/low or CIT naïve for each treatment arm which proceeds to Phase 2 and test H_0 : ORR $\leq 27\%$ against H_1 : ORR $> 27\%$ for PD-L1 high of CIT naïve.

Patients who cannot be assessed for response will be counted as non-responders.

The primary analysis will be conducted using the FAS with supportive analyses presented using the CAE population.

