11.1.6.2.1 Clinical Benefit Rate (CBR)

Descriptive statistics for CBR, confirmed CR, PR or SD based on the response assessments by the Investigator will be presented by strata and treatment arm using both the FAS and the CAE population. Exact 95% Clopper-Pearson CIs for CBR will also be presented.

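### SAP 4.1.4 relaxes the SD part of CBR to one scan at 42 days or later, and no CBR under the protocol's two-assessment, 14-week rule is planned

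*SAP*

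**What the plan says.** Protocol 9.4.2 defines CBR as confirmed CR or PR, or SD "documented during at least 2 on-study assessments and including at least 14 weeks on study". Its worked example allows two weeks around the Week 17 assessment.

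SAP 4.1.4, under the changes from protocol, reproduces that definition and amends its later part "to allow for at least one on-study assessment at least 42 days on study". The reason given is alignment with SAP 8.2.

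The operative text in SAP 8.2.3 reads "CBR is defined as the proportion of patients documented to have a confirmed CR or PR, or SD". It has no duration or second-scan condition of its own; the 42 days enter through the best overall response (BOR) rules in SAP 8.2.1. For a first reading of CR, PR or SD followed by PD, note (1) there says "Best response will be SD if the first response is after 42 days on-treatment". For CR, PR or SD followed by NE, note (2) says "Best response will be SD if the first response is after 42 days on-study". For an unconfirmed CR or PR that cannot be confirmed "due to dropping off study, the best overall response will be SD".

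SAP 11.1.6.2.1 plans "Descriptive statistics for CBR, confirmed CR, PR or SD based on the response assessments by the Investigator", in the FAS and the CAE population with exact CIs, under this one definition. SAP 11.1.6.1 tabulates ORR and the BOR categories in the same two populations.

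**The concern.** The protocol set a stricter rule for CBR than for best response. SD had to hold through a second assessment, about 16 weeks into treatment. The SAP drops that condition, and CBR becomes a statement that disease had not progressed at one scan.

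Two things follow. A reader who knows the protocol will take the reported CBR as evidence of control over two scans, which it is not. And the SAP's CBR repeats the CR, PR and SD rows of the BOR table; apart from its CI it adds nothing to them. The protocol's own secondary endpoint would go unreported as defined.

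**Working it through.** **Inputs.** Disease evaluations every 8 weeks from Cycle 1 Day 1, ±10 days (Protocol Table 1, disease evaluation footnote; same in the SAP). SAP floor: 42 days. Protocol floor: two assessments and 14 weeks = 14 × 7 = 98 days.

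**The documents' own figures.** Week 17 is 16 completed weeks; 16 − 2 = 14 weeks, as in Protocol 9.4.2. The second scan plus its window is 16 × 7 + 10 = 122, the number that SAP 11.1.6.2.3 calls Study Day 122. In elapsed days this agrees. If first dose is Day 1, 122 days later is Study Day 123. Nothing below depends on that one day.

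**Scan windows in days after first dose.**
- First scan: 56 ± 10 = 46 to 66. The earliest is 46 − 42 = 4 days past the SAP floor.
- Second scan: 112 ± 10 = 102 to 122. The earliest is 102 − 98 = 4 days past the protocol floor.

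Neither time floor removes an on-schedule scan. The condition that matters is the dropped second assessment.

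**Patient patterns with on-schedule scans** (the protocol qualifier is read as applying to SD only):

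| Week 8, then week 16 | SAP best response | In SAP CBR | In protocol CBR |
|---|---|---|---|
| SD, then PD | SD | yes | no |
| CR or PR, then PD | SD | yes | no |
| SD, then no later evaluable scan | SD | yes | no |
| CR or PR, then drop-out | SD | yes | no |
| SD, then SD | SD | yes | yes |
| PR, then SD, never confirmed | SD | yes | depends on reading |
| Confirmed CR or PR | CR or PR | yes | yes |
| PD at week 8 | PD | no | no |

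**Direction.** A patient counted by the protocol rule has either a confirmed CR or PR, or an SD scan at day 46 or later before progression. Either way the SAP best response is SD or better, so the SAP counts the patient too. In the same population the SAP rate cannot be lower. If the protocol qualifier also covered CR and PR, the protocol rate would be the same or lower still.

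**Landmark PFS rates** (SAP 11.1.6.2.3, months of 30.4375 days):
- 3 months = 91.3 days, between the first window (ends day 66) and the second (starts day 102).
- 6 months = 182.6 days, after the third window (168 ± 10 = 158 to 178).

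PD first seen at an on-schedule second scan is therefore not yet in the 3-month rate. It is in the 6-month rate, together with PD from the third scan.

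**The case against.** The change is declared in the right place, beside the protocol wording. Section 9 of the protocol lets the SAP modify plans and asks for an amendment only for major changes to the primary endpoint; CBR is secondary. The 42 days match the protocol's own 6-week minimum for a best response of SD in Appendix 4. CBR has no hypothesis test, and expansion decisions use ORR. All of this stands, so a reader who inferred a hidden or forbidden change would be wrong.

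A reader might also infer that no planned output shows control past the second scan. The documents do not support that. SAP 11.1.6.2.3 summarizes PFS in the same manner as duration of response, which SAP 11.1.6.2.2 gives with quartiles and Kaplan–Meier plots. The PFS curve can be read at any time, including after day 122. It is still indirect. It includes responders and deaths, and a patient with SD at week 8 and no later scan is censored (unless death follows within 122 days), whereas the SAP's CBR counts that patient as benefit.

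Nor is it a defect in itself that every on-schedule first scan clears the floor. The same holds for the Appendix 4 rule at the first scan and for the 14-week floor at the second.

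Finally, the protocol sentence is not fully specified. It does not say whether the qualifier covers SD only, and read literally it would exclude an unconfirmed PR followed by SD. That stands, and the fix has to settle it.

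**Conclusion.** The point holds as a cheap improvement. The SAP openly replaces the two-assessment, 14-week condition with a single scan at 42 days or later. With on-schedule scans its CBR is equal to or higher than the protocol's and equals CR + PR + SD from the BOR table. No CBR under the protocol definition appears in the SAP text; table shells are not in the file.

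The size is unknown. The documents give no SD rate, and an assumed PFS curve would not supply one: it would include confirmed responders, who count under both rules, and miss patients with SD and no later evaluable scan, who count only under the SAP. A reader might infer a material inflation of CBR; the documents support the direction only.

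The conclusion assumes on-schedule scans and the same population for both rates.

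**What to change.** In SAP 8.2.3 and 11.1.6.2.1, add a supportive CBR by the protocol definition: confirmed CR or PR, or SD on two or more on-study assessments spanning 14 weeks or more on study. Present it in the FAS and the CAE population beside the 42-day rate, and label each row with its definition. State three rules with it:
- the qualifier is applied to SD only;
- an assessment with an unconfirmed CR or PR counts as SD or better;
- how an NE between two qualifying assessments is handled.

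The final SAP version that SAP 4.0 foresees before database lock is a natural place for this. The cost is SAP wording, these stated rules and one more derived variable from scans already collected. The downside for the sponsor is a CBR that is the same or lower, shown beside the current one.

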4.1.5 Sitravatinib Pharmacokinetic Sub-Studies

Two Sitravatinib sub-studies were added to protocol v4.0, however as per the project administrative letter, dated July 15th 2020;

- PK Formulations of capsules (Appendix 5 of protocol v6):

This was intended to be an evaluation of Sitravatinib PK using three formulations of capsules. The objective of this sub-study was fulfilled in a healthy volunteer study (516-006) which demonstrated bioequivalence between the 100 mg Sitravatinib malate capsule formulation (test) and the 120 mg Sitravatinib free base capsule formulation (reference). Therefore, no additional data are needed.

- PK Food sub-study (Appendix 6 of protocol v6):

This was intended to be an evaluation of PK when Sitravatinib capsules are administered orally in the fed state. Mirati Therapeutics has decided to conduct a separate study to evaluate the pharmacokinetics of Sitravatinib with and without food. Therefore, the Pharmacokinetic Food Effect Sub-Study (Appendix 6) will be closed.

As a result, the PK sub-study component of this study will be comprised of selected Demographic and Safety summaries, as described in Section 11.2. Patients from these PK sub-studies will be excluded from the main study summaries, their data will be listed separately.

4.2 Study Treatment Definitions

4.2.1 Study Drug

The investigational agents of primary interest (Glesatinib, Sitravatinib, Mocetinostat) are referred to in the protocol as both study drugs and study treatments. Within the context of this SAP these terms are used interchangeably.

4.2.2 Treatment Arm

The combination of Nivolumab and one of the investigational study treatments (including dose level) will be referred to as the “treatment arm”.

5.0 Study Objectives and Endpoints

5.1 Objectives

5.1.1 Primary Objective

- To evaluate the clinical activity of Nivolumab in 3 combination regimens with the investigational agents Glesatinib, Sitravatinib, or Mocetinostat, in patients with non-squamous non-small cell lung cancer (NSCLC).

5.1.2 Secondary Objectives

- To evaluate the safety and tolerability of the combination regimens in the selected population.
- To evaluate secondary efficacy endpoints of the combination regimens in the selected population.
- To evaluate the PK of the investigational agents administered in combination with Nivolumab.
- To evaluate the PK of different Sitravatinib capsule formulations.
- To evaluate the PK of Sitravatinib administered with food.

5.1.3 Exploratory Objectives

- [REDACTED]
- [REDACTED]
- [REDACTED]

5.2 Endpoints

5.2.1 Primary Endpoint

The primary endpoint is the Objective Response Rate (ORR) as defined by Response Evaluation Criteria in Solid Tumors (RECIST) v1.1.

5.2.2 Secondary Endpoints

- Safety characterized by type, incidence, severity, timing, seriousness and relationship to study treatment of adverse events (AEs), and laboratory abnormalities.
- Secondary efficacy endpoints

- Duration of Response (DoR)
- CBR
- Progression-Free Survival (PFS)
- 1-Year Survival Rate
- Overall Survival (OS)
- Blood plasma concentrations of the investigational agents.

5.2.3 Exploratory Endpoints

6.0 Study Design

Study MRTX-500 is an open-label, parallel Phase 2 evaluation of Nivolumab in combination with three investigational agents, Glesatinib, Sitravatinib or Mocetinostat, in patients with locally advanced, unresectable or metastatic non-squamous NSCLC. Patients who have experienced progression of disease on or after treatment with a checkpoint inhibitor (checkpoint inhibitor therapy [CIT]-experienced) as well as those who have experienced disease progression after platinum-based doublet chemotherapy (CIT-naïve) will be enrolled. The primary objective is to evaluate the clinical activity of the combination study treatments using ORR in accordance with RECIST 1.1.

Secondary objectives include evaluation of safety, secondary efficacy endpoints, and PK for the investigational agents. The Schedule of Assessments to be performed in the study is presented in Table 1. Pharmacokinetic and blood biomarker sample collection and triplicate Electrocardiogram (ECG) assessment time points are presented in Table 2, Table 3, and Table 4.

Specifics of two Sitravatinib sub-studies are presented in the protocol appendices, including the PK evaluation of three Sitravatinib capsule formulations (Appendix 5) and the PK of Sitravatinib administered with food (Appendix 6).

The treatment arms included in this study are the following:

1. Glesatinib plus Nivolumab.
2. Sitravatinib plus Nivolumab.
3. Mocetinostat plus Nivolumab.

To control bias in assignment of individual patients to treatment arms and to mitigate the risk of medication errors with the three investigational study treatments administered in specific regimens, study sites will be aligned with one specified treatment combination. Site alignment may change as patient cohorts are filled or patient recruitment factors shift at sites.

Table 1: Schedule of Assessments

Assessments	Screen/ Baseline	Cycle 1		Cycle 2 and 3		≥ Cycle 4		End of Treatment ¹⁵	
	Within 28 days	Day 1 (± 2 days)	Day 15 (± 2 days)	Day 1 (± 2 days)	Day 15 (± 2 days)	Day 1 (± 2 days)	Day 15 (± 2 days)	End of Treatment/ Withdrawal	Post Treatment Follow Up
Study Participation Informed Consent ¹	Before study specific assessments								
Tumor Tissue Collection for PD-L1 Expression and Tumor Gene Alterations ²	X								
Medical History, Disease History, Prior Therapy	X								
ECOG Performance Status	X								
Physical Exam ³	X							X	
Abbreviated Physical Exam ³	X	X	X	X	X	X	X		
Vital Signs ⁴	X	X	X	X	X	X	X	X	
Pregnancy Test ⁵	X								
Hematology ^{6,7}	X	X	X	X	X	X	X	X	

As clinically indicated

Table 1: Schedule of Assessments (Continued)

Assessments	Screen/ Baseline		Cycle 1		Cycle 2 and 3		≥ Cycle 4		End of Treatment ¹⁵	
	Within 28 days	Day 1 (± 2 days)	Day 15 (± 2 days)	Day 1 (± 2 days)	Day 15 (± 2 days)	Day 1 (± 2 days)	Day 15 (± 2 days)	Day 15 (± 2 days)	End of Treatment/ Withdrawal	Post Treatment Follow Up
Coagulation ^{6,7}	X								As clinically indicated	
Urinalysis ^{6,7}	X								As clinically indicated	
Serum Chemistry ^{6,7}	X	X	X	X	X	X	X	X		X
Thyroid Function Test ^{6,7}	X	X		X			X			X
Blood for Pharmacokinetics ⁸										
Biopsy of Tumor for Biomarker Studies (Optional) ⁹										
Blood Samples – Flow Cytometry ¹⁰										
Blood Samples – Protein and Cytokine Biomarkers ¹⁰										
ctDNA blood sample ¹¹	X									
Single 12-Lead ECG ¹²	X									
Triplete 12-Lead ECG ¹²										

See Table 2, Table 3, and Table 4 and Table 4 and Table 23, Table 24, Table 25 from the protocol sub-study appendix 5 and appendix 6 for PK sub-studies

Table 1: Schedule of Assessments (Continued)

Assessments	Screen/ Baseline	Cycle 1		Cycle 2 and 3		≥Cycle 4		End of Treatment ¹⁵	
	Within 28 days	Day 1 (± 2 days)	Day 15 (± 2 days)	Day 1 (± 2 days)	Day 15 (± 2 days)	Day 1 (± 2 days)	Day 15 (± 2 days)	End of Treatment/ Withdrawal	Post Treatment Follow Up
Echocardiogram (Mocetinostat and Sitravatinib Treatment Arms Only)	X		X Mocetinostat arm only	X Cycle 3 only		X Mocetinostat arm only		X	
Disease Evaluation ¹³	X				Every 8 weeks (± 10 days) for ~1 year and then every 16 weeks				
Investigational Agent Dispensing and/or Reconciliation		X		X		X			
Nivolumab Administration		X	X if Q2W	X	X if Q2W	X	X if Q2W		
Adverse Events ¹⁴ and Concomitant Medications	SAEs only								
Long Term Follow-up ¹⁶					Throughout				X

- 1 Study Participation Informed Consent: May be performed more than 28 days prior to the first dose of study treatment and must be completed prior to initiation of any study specific assessments.
- 2 Tumor Testing for PD-L1 Expression and Tumor Gene Alterations: Encouraged for all patients. Archival tumor tissue allowed. For patients enrolled in CIT Naïve cohorts, the sample must have been collected following the completion of the most recent systemic treatment regimen and the central laboratory testing is to begin prior to study entry. Biopsy may precede informed consent if performed as Standard of Care (SOC) or to assess eligibility for a different clinical trial.
- 3 Physical Examinations: A complete physical examination required at Screening and End of Treatment only. Height will be recorded at screening only. All other evaluations will be symptom-directed, abbreviated evaluations.
- 4 Vital Signs: Weight, temperature, blood pressure, and pulse rate to be assessed prior to dosing as indicated.
- 5 Pregnancy Test: If the patient is a woman of childbearing potential, negative serum or urine pregnancy test performed by the local laboratory at screening will be required. The informed consent process must include discussion of the risks associated with pregnancy and adequate contraception methods. Additional pregnancy testing may be necessary if required by local practices or regulations, or if potential pregnancy is suspected.
- 6 Selected Day 1 Assessments: Repeat assessment not required if screening assessment performed within 7 days before the first dose.
- 7 Safety Laboratory Assessments: Hematology, coagulation, chemistry, thyroid function and urinalysis evaluations (see Table 19 in the protocol) will be performed by local laboratories.

8 Pharmacokinetic Samples: Blood samples to be collected following ECGs and assessment of vital signs as scheduled in Table 2, Table 3, and Table 4. In addition, unscheduled PK blood samples should be drawn in association with two kinds of safety events: 1) as soon as possible after a Serious Adverse Event (SAE), and 2) at a clinic visit at least one week following a dose modification of the investigational agent.

9 Tumor Biopsy for Biomarker Studies: Consent for serial sampling of tumor tissue (preferably the same lesion) is requested but is not mandatory for study entry. If tumor biopsy has been performed during screening, then that biopsy may be used for the baseline assessment. Markers of interest in tumor tissue include PD-L1 expression, CD8+ tumor infiltrating lymphocytes (TILs) including proliferating (Ki67+) CD8+ cells, natural killer cells (NK-cells), T regulatory cells (Tregs), macrophages and myeloid derived suppressor cells (MDSCs). Gene expression analyses may also be performed.

10 Blood Samples for Biomarker Studies: Blood samples for flow cytometry and protein/cytokine assays will be collected as outlined in Table 2, Table 3, and Table 4. Markers of interest in circulation include circulating PD-L1, Tregs, MDSCs, NK-cells, flow cytometry for T- and B-cell including CD4, CD8 and Ki67, monocytes and selected cytokines including CD8A, GZMB, IFN γ , CXCL9, CXCL10, CXCL11, and TBX21. Patients participating in the Sitravatinib formulation and food effect sub-studies described in protocol Appendix 5 and Appendix 6 are exempt from sample collection for biomarker studies, including flow cytometry and protein/cytokine assays.

11 Blood samples for ctDNA analysis: Blood will be collected in two 10ml Streck brand Cell-Free DNA Blood Collection tubes allowing shipping and stability at ambient temperatures.

12 12-Lead ECGs: Triplicate ECGs will accompany PK sampling as described in Table 2, Table 3, and Table 4. Only for the Mocetinostat containing treatment arm, ECGs are to be performed on Day 1 of each cycle, either as a triplicate ECG accompanying PK or as a single ECG. In addition, ECGs are to be performed as clinically indicated. Assessments will include an evaluation of rhythm, heart rate, and PR, QRS, QT, and QTc intervals. rRR interval should be recorded during each ECG assessment in order to calculate QTcF.

13 Disease Evaluations: To be performed at screening (28 day window allowed) and every 8 weeks from Cycle 1 Day 1 (\pm 10 days window for all other assessments except screening) until Week 49 (~1 year) and then every 16 weeks. All on-study disease evaluations should be based on a calendar beginning from the first day of dosing. At screening/baseline, assessments are to include CT with contrast of the chest, abdomen and pelvis, as well as brain Magnetic Resonance Imaging (MRI) with and without gadolinium or Computed Tomography Scan (CT) with contrast, a whole body bone scan and evaluation of any superficial lesions. Subsequent disease assessments should include all sites of disease identified at baseline or suspected to have developed; bone scans may be performed half as often (every 16 weeks) as other radiology evaluations and should be performed during assessment for confirmation of disease response. More detailed guidance on exceptional circumstances is provided in the protocol.

14 Adverse Events: SAEs will be reported from the time of informed consent until at least 28 days after the last administration of investigational agent or Nivolumab. Adverse events will be reported from the first day of study treatment until at least 28 days after last dose of study drug, and until resolution or stabilization of acute AEs and/or ongoing SAEs.

15 End of Treatment: All patients will be followed for AEs for at least 28 days after the last dose of Study Treatment. Assessments that have been completed in the previous 4 weeks do not need to be repeated (8 or 16 weeks for tumor assessments in accordance with schedule).

16 Long Term Follow-up: Survival status and subsequent therapies will be collected during long term follow-up every 2 months (\pm 14 days) from the End of Treatment visit until death or lost to follow-up. Follow-up may be performed by telephone contact.

Table 2: Glesatinib Schedule of PK, Biomarker Samples and Triplicate ECG Assessments

	Screen/ Baseline	Cycle 1 Day 1				Cycle 1 Day 15 (± 2 days)		Cycle 2, 3, 5 Day 1 (± 2 days)		Cycle 2 Day 15 (± 2 days)	
Collection Time and Allowable Window	Within 28 days	Pre-dose (-0.5-0 hour)	30 min (± 10 min)	3 hour (2-4 hour)	6 hour (5-8 hour)	Pre-dose (-0.5-0 hour)	Pre-dose (-0.5-0 hour)	Pre-dose (-0.5-0 hour)	Pre-dose (-0.5-0 hour)	Pre-dose (-0.5-0 hour)	
PK Sample ¹		X	X	X	X	X	X	X	X	X	
Flow Cytometry ²	X	X					X				
Protein and Cytokine Biomarkers ²		X					X				
Triplicate ECG ³		X			X	X	X	X	X	X	

¹ Scheduled vital signs and triplicate ECGs precede PK sample collection in all cases. Glesatinib dosing and sampling should precede Nivolumab infusion.
² The Day 1 blood samples for biomarker studies may be drawn up to 2 hours before dosing. The screen/baseline sample should not be collected on the same day as the pre-dose Cycle 1 Day 1 sample.

³ ECGs should be taken in triplicate, each reading at least 2 minutes apart. On Cycle 1 Day 1, two sets of triplicate ECGs should be done within 30 minutes prior to dosing (e.g., at 15 minute intervals) to firmly establish the baseline for the patient. In general, ECGs should be performed prior (within -30 to -5 minutes) to the respective PK blood collection.

Table 3: Sitravatinib Schedule of PK, Biomarker Samples and Tripligate ECG Assessments

	Screen/ Baseline	Cycle 1 Day 1			Cycle 1 Day 15 (± 2 days)		Cycle 2, 3, 5 Day 1 (± 2 days)		Cycle 2 Day 15 (± 2 days)	
Collection Time and Allowable Window	Within 28 days	Pre-dose (-0.5-0 hour)	30 min (± 10 min)	4 hour (3-5 hour)	6 hour (5.5-8 hour)	Pre-dose (-0.5-0 hour)	Pre-dose (-0.5-0 hour)	Pre-dose (-0.5-0 hour)	Pre-dose (-0.5-0 hour)	Pre-dose (-0.5-0 hour)
PK Sample ^{1, 4}		X	X	X	X	X	X	X	X	X
Flow Cytometry ^{2, 5}	X	X				X				X
Protein and Cytokine Biomarkers ^{2, 5}		X				X				
Tripligate ECG ^{3, 6}		X	X	X	X		X	X	X	X

¹ Scheduled vital signs and tripligate ECGs precede PK sample collection in all cases. Sitravatinib dosing and sampling should precede Nivolumab infusion.
² The Day 1 blood samples for biomarker studies may be drawn up to 2 hours before dosing. The screen/baseline sample should not be collected on the same day as the pre-dose Cycle 1 Day 1 sample.

³ ECGs should be taken in tripligate, each reading approximately 2 minutes apart. On Cycle 1 Day 1 only, two sets of tripligate ECGs should be done within 1 hour prior to dosing (e.g., at 30 minute intervals prior to dosing) to firmly establish the baseline for the patient. One set of tripligate ECGs is required at all other time points. In general, ECGs should be performed prior to the respective PK blood collection. Examples of the schedule are presented below:

- o Example for Cycle 1 Day 1 pre-dose ECGs/PK: ~1.0 hr (Tripligate ECGs); ~30 mins (Tripligate ECGs); ~15 mins (Vitals/PK).

- o Example for all other pre-dose ECG/PK assessments: ~30 mins (Tripligate ECGs); ~15 mins (Vitals/PK).

⁴ Sample schedules for Sitravatinib formulation and food effect evaluations are presented in protocol Appendix 5 and Appendix 6, Table 22, Table 23, Table 24, and Table 25.

⁵ Patients participating in the Sitravatinib formulation and food effect sub-studies described in protocol Appendix 5 and Appendix 6 are exempt from sample collection for biomarker studies, including flow cytometry and protein/cytokine assays.

⁶ Patients participating in the Sitravatinib formulation and food effect sub-studies described in protocol Appendix 5 and Appendix 6 will undergo evaluation by tripligate ECG on Lead-In Day 1 instead of Cycle 1 Day 1.

Table 4: Mocetinostat Schedule of PK, Biomarker Samples and Triplicate ECG Assessments (Study arm not initiated)

	Screen/ Baseline	Cycle 1 Day 1			Cycle 1 Day 15 (± 2 days)			Cycle 2, 3, 5 Day 1 (± 2 days)	
Collection Time and Allowable Window	Within 28 days	Pre-dose (-0.5-0 hour)	1 hour (0.5-1.5 hour)	3 hour (2-4 hour)	7 hour (6-8 hour)	Pre-dose (-0.5-0 hour)	1 hour (0.5-1.5 hour)	Pre-dose (-0.5-0 hour)	1 hour (0.5-1.5 hour)
PK Sample ¹	X	X	X	X	X	X	X	X	X
Flow Cytometry ²	X	X				X			
Protein and Cytokine Biomarkers ²		X				X			
Triplicate ECG ³		X	X			X		X	X

1 Scheduled vital signs and triplicate ECGs precede PK sample collection in all cases. On days Mocetinostat and Nivolumab are both administered and scheduled for PK assessment, Mocetinostat dosing and sampling should precede Nivolumab infusion.

2 The Day 1 blood samples for biomarker studies may be drawn up to 2 hours before dosing. The screen/baseline sample should not be collected on the same day as the pre-dose Cycle 1 Day 1 sample.

3 ECGs should be taken in triplicate, with readings at least 2 minutes apart. On Cycle 1 Day 1, two sets of triplicate ECGs should be done within 30 minutes prior to dosing (e.g., at 15 minute intervals) to firmly establish the baseline. In general, ECGs should be performed prior (within -30 to -5 minutes) to the respective PK blood collection.

